#### 9.2 SAMPLE SIZE DETERMINATION

#### 9.2.1 Historical data and assumptions

Results from a previous intra-individual trial designed as a right-left comparison of Adapalene 0.1% - BPO 2.5% gel versus vehicle gel in acne subjects (protocol RD.03.SPR.40183E) showed a standard deviation (SD) of the bilateral differences in terms of *total atrophic acne scar count* at week 24 of around 4.8 with a mean bilateral difference around 2.

#### 9.2.2 Sample size calculation

Using the historical data mentioned above, 50 evaluable subjects will be required, with 80% power. To allow about 20% rate of subjects excluded from analysis (major deviation, drop out, lost to follow-up, etc.) at week 24, 60 subjects should be enrolled.

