# Principal statistical methods and sample size calculation:

The Per Protocol (PP) population will consist of all enrolled and randomized subjects, except subjects who have major deviations from the protocol. The Intent-to-Treat (ITT) population will consist of the entire population enrolled and randomized. The last observation carried forward (LOCF) method will be used to impute missing values of acne scar and lesion counts and global assessment scores. Analysis population definitions will be decided before the database lock and unblinding.

The primary objective of this trial is to demonstrate the superiority of Adapalene 0.3% - BPO 2.5% gel compared to its vehicle, in terms of total atrophic acne scar count at week 24.

The mean bilateral difference between products of primary efficacy endpoint will be analyzed by using the Wilcoxon Rank Signed test, testing the hypothesis of equality. The p-value will have to be inferior to 0.05 at week 24, on ITT/LOCF population. PP analysis will be also performed to assess the robustness of the results obtained on the ITT/LOCF population.

The other efficacy variables of part I will be analyzed similarly as primary analysis on appropriate population. Each test will be

Clinical trial title: Effect of Adapalene 0.3% - benzoyl peroxide 2.5% gel versus vehicle gel on the risk of formation of atrophic acne scars in moderate to severe acne subjects

**Short title:** Adapalene 0.3% - benzoyl peroxide 2.5% gel and risk of formation of atrophic acne scars

two-sided, at the 0.050 significance level.

The subject characteristics (previous medication, concomitant medication, demographics, baseline characteristics...), lesion counts, microrelief, adverse events, local tolerability and questionnaires, and all variables of part II will be summarized by descriptive statistics (usual statistics and frequency distribution).

Results from a previous intra-individual trial designed as a right-left comparison of Adapalene 0.1% - BPO 2.5% gel versus vehicle gel in acne subjects (protocol RD.03.SPR.40183E) showed a standard deviation (SD) of the bilateral differences in terms of *total atrophic acne scar count* at Week 24 of around 4.8 with a mean bilateral difference around 2.

Using the historical data mentioned above, 50 evaluable subjects will be required, with 80% power. To allow about 20% rate of subjects excluded from the analysis (drop out, lost to follow-up, etc.) at week 24, 60 subjects should be enrolled.

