#### 9.1.2.1 The Per Protocol efficacy population (PP)

This population will consist of all enrolled and randomized subjects, except subjects who have major deviations from the protocol. Major deviations will be defined during a data review meeting after data entry and before unblinding the clinical trial treatment. Major protocol deviations will be considered as having a possible effect on the interpretation of primary efficacy results and may include: inclusion criteria not respected, non-available efficacy assessment, interfering therapy at inclusion, etc.

The primary efficacy endpoint will be analyzed based on this population.

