#### 9.1.2.2 The Intent-to-Treat efficacy population (ITT)

This population will consist of the entire population enrolled and randomized (i.e., assigned a kit number). The ITT population will be used for all variables except the safety variables.

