#### 9.1.2.4 Missing values

The last observation carried forward (LOCF) method will be used to impute missing values of acne scar and lesion counts and global assessment scores (SGA and IGA) during part I. If no post-baseline data are available, baseline will be carried forward. The other missing values of part I and the data collected during part II will not be replaced (observed data).

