#### 9.1.4 Statistical analyses

The primary objective of this trial is to demonstrate the superiority of Adapalene 0.3% - BPO 2.5% gel compared to its vehicle, in terms of total atrophic acne scar count at week 24. The mean bilateral difference between products of primary efficacy endpoint will be analyzed by using the Wilcoxon Rank Signed test, testing the hypothesis of equality. The p-value will have to be inferior to 0.05 at week 24, on ITT/LOCF population. Per Protocol analysis will be also performed to assess the robustness of the results obtained on the ITT/LOCF population.

GALDERMA RESEARCH & DEVELOPMENT Protocol N° RD.03.SPR.105061 Page 75 of 99 CONFIDENTIAL

The other efficacy variables of part I will be analyzed similarly as the primary analysis on the appropriate population. Each test will be two-sided, at the 0.050 significance level.

The subject characteristics (previous medication, concomitant medication, demographics, baseline characteristics...), lesion counts, microrelief, adverse events, local tolerability and questionnaires and all variables of part II will be summarized by descriptive statistics (usual statistics and frequency distribution).

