5.2 PER PROTOCOL POPULATION (PP)

The PP Population is defined as comprising the ITT subjects who have no major protocol deviations that will be refined during a blind review meeting. Only the primary efficacy endpoint will be analyzed based on this population.

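### 60 enrolled less the stated loss of about 20% leaves 48 evaluable subjects, not the required 50; 60 covers a loss of only about 17%

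*Protocol*

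**What the plan says.** The sample size rests on an earlier split-face trial of the lower-strength gel, in which the SD of the bilateral difference in total atrophic scar count was "at week 24 of around 4.8 with a mean bilateral difference around 2" (Protocol 9.2.1, repeated in SAP 3.2.1). From this, Protocol 9.2.2 and SAP 3.2.2 state "50 evaluable subjects will be required, with 80% power. To allow about 20% rate of subjects excluded from analysis", and arrive at 60 to be enrolled. The synopsis gives the same figures: "To allow about 20% rate of subjects excluded from the analysis (drop out, lost to follow-up, etc.) at week 24". It differs only in its examples of exclusions, which omit major deviations.

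None of the three places names the test or the significance level used. Protocol 9.1.4 and SAP 6.3.1 name a Wilcoxon signed-rank test on the bilateral difference, and Protocol 9.1.4 and SAP 6 set two-sided 0.05. The success rule is "The p-value will have to be inferior to 0.05 at week 24, on ITT/LOCF population". The Per Protocol analysis is a robustness check.

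**The concern.** The three numbers are offered as one chain: 50 needed, about 20% lost, therefore 60 enrolled. If 20% of 60 are lost, the trial ends with fewer evaluable subjects than it says it needs. The 60 looks like 50 increased by 20%, where the requirement should have been divided by the share expected to remain. What is at stake is whether the stated evaluable number, and the 80% power attached to it, are delivered at the stated loss rate. The statement stands in both documents, so a reader checking either one meets the same mismatch.

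**Working it through.** **Inputs.** Mean difference 2 and SD 4.8 (Protocol 9.2.1). Two-sided 0.05 and the signed-rank test (Protocol 9.1.4). Power 80%, 50 evaluable, loss 20%, 60 enrolled (Protocol 9.2.2).

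**1. Reproducing the 50.**
- Normal approximation: n = ((1.960 + 0.842) x 4.8 / 2)^2 = 45.2, so 46.
- Paired t with the noncentral t distribution: power is 79.9% at 47 and 80.7% at 48, so 48.
- Signed-rank, dividing the paired-t number by its efficiency under normality (3/pi = 0.955): 48 / 0.955 = 50.3.
- Simulated signed-rank power at 50 with normal differences: 80.8%.

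So 50 is reproduced, and it fits the signed-rank test named in the plan.

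**2. From 50 to 60.**
- Required number divided by the share kept: 50 / (1 - 0.20) = 62.5, so 63.
- Required number increased by 20%: 50 x 1.20 = 60, the plan's figure.
- Evaluable subjects left from 60 after a 20% loss: 60 x 0.80 = 48.
- Loss that leaves exactly 50: 1 - 50/60 = 16.7%.

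**3. What two subjects cost.**

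| Evaluable n | Signed-rank power | Paired-t power |
|---|---|---|
| 48 | 78.8% | 80.7% |
| 50 | 80.8% | 82.3% |

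The signed-rank figures are simulated (normal differences, exact critical values, 100,000 replicates, standard error about 0.1 points). The loss is 80.8 - 78.8 = 2.0 points by signed-rank and 82.3 - 80.7 = 1.6 points by paired t.

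**4. Which analyses are touched.** The ITT set is defined without exclusions: "This population will consist of the entire population enrolled and randomized (i.e., assigned a kit number". Missing scar counts are filled by LOCF, and "If no post-baseline data are available, baseline will be carried forward" (Protocol 9.1.2.4). SAP 5.4 adds that the number of subjects is the same at every visit. The deciding test therefore uses all 60, whatever the loss. Neither document defines the evaluable set. It is probably close to Per Protocol, since Protocol 9.1.2.1 gives as possible major deviations "inclusion criteria not respected, non-available efficacy assessment, interfering therapy at inclusion, etc". SAP 5.2 limits the use of that population: "Only the primary efficacy endpoint will be analyzed based on this population".

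**The case against.** The best defence is that every input is approximate. The loss is about 20%, the SD around 4.8 and the mean around 2. If rounding alone lets the SD run from 4.75 to 4.85 and the mean from 1.95 to 2.05 (an assumed range), the paired-t requirement runs from 45 to 51, a wider spread than the two-subject gap. The sample-size section names no test, and by paired t 48 subjects still give 80.7% power. On that base the chain even closes, since 48 / 0.80 = 60.

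This limits the size of the point: the printed 50 is missed, and the 80% target is missed only by the signed-rank calculation, by about one point. It does not reconcile the figures. The plan prints 50, not 48, and 50 with 60 implies 16.7%. The named test is the signed-rank, for which 50 is about where 80% is reached.

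A reader might go further and infer that the primary test is underpowered, or that the plan errs by giving no power for ITT/LOCF. The documents do not support either reading. Protocol 9.2.2 ties its 80% to evaluable subjects, and sizing on those while testing everyone randomised is not a contradiction. Carried-forward values could dilute the effect, but the documents give no share of subjects carried forward, no effect retained and no SD for such values, so no deficit can be shown.

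**Conclusion.** The statement is wrong as written, and the error is minor. At 20% loss, 60 enrolled gives 48 evaluable, two short of the stated requirement; 60 holds 50 only up to 16.7% loss. The cost is about two power points in analyses made after exclusions: about 79% against about 81% by signed-rank, or 80.7% against 82.3% by paired t. These figures assume normal differences with mean 2 and SD 4.8 and two-sided 0.05.

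The ITT/LOCF primary test is not affected. The 80% applies to the evaluable set; at n = 60 the ITT/LOCF test would have about 87% signed-rank power if mean 2 and SD 4.8 held for all 60.

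**What to change.** Keep 60 enrolled. In the Protocol synopsis, Protocol 9.2.2 and SAP 3.2.2, make one of two changes:

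- keep the 20% and state that it leaves 48 evaluable, with about 79% power by signed-rank (about 81% by paired t); or
- keep the 50 and state that 60 enrolled secures it only up to about 17% loss. This describes what 60 can bear; it is not a forecast that 17% will be lost.

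In either case, name the test behind the calculation. If wanted, add one sentence that the 80% refers to the evaluable set, with the 87% figure for n = 60 and its condition. No further assumptions from the sponsor are needed.

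The cost is wording in three places. Enrolment, the test and the success rule stay as they are. The first option prints a slightly less favourable power; the second prints a smaller tolerated loss.

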#### 10 TRAINING / MONITORING / DATA MANAGEMENT / QUALITY ASSURANCE

A contract research organization (CRO) will be responsible for monitoring the clinical trial and the sponsor may perform co-monitoring visits at selected sites.

#### 10.1 Personnel training

Clinical Research Associates (CRA) will be trained prior to clinical trial initiation and as needed during the trial (in particular in case of protocol amendment). During this training, an overview of the disease of interest and treatment will be presented. Specific monitoring guidelines and procedures to be followed during monitoring visits will be discussed.

Initiation visits will be conducted with all principal investigators and site teams. During these visits, an extensive review and discussion of the protocol, procedures and eCRF will be conducted. Evaluation scales will also be reviewed

A monitoring manual will be provided to each CRA as an additional reference tool.

An eCRF completion guideline will be provided to each CRA and site. These guidelines will contain instructions on how to fill in the eCRF with some examples in order to standardize the eCRF completion as much as possible.

A trial reference manual will be provided to each site as an additional reference tool. These guidelines will contain key CRO and sponsor contacts and phone numbers and specific instructions for site in order to standardize as much as possible the assessments performed during the clinical trial. A manual will also be provided to the product dispenser, with specific instructions detailing use of the "study companion" tablet.

Furthermore during the investigator meeting a specific training on scars assessments will be conducted.

#### 10.2 CLINICAL MONITORING

The conduct of the clinical trial will be closely monitored by GALDERMA R&D or representatives to verify the adherence to the clinical trial protocol, ICH-GCP regulations, applicable standard operating procedures (SOPs), guidelines, and all local regulations.

The investigator will allow representatives of GALDERMA R&D to have direct access to all clinical trial records, eCRFs, corresponding subject medical records, investigational product dispensing

GALDERMA RESEARCH & DEVELOPMENT Protocol N° RD.03.SPR.105061 Page 77 of 99 CONFIDENTIAL

records and investigational product storage area, site facilities and any other documents considered as source documentation.

The investigator also agrees to assist the CRO/ GALDERMA R&D representatives, if required.

#### 10.3 DATA MANAGEMENT

A CRO will be responsible for data management in connection with the sponsor's data manager.

All data management procedures will be detailed in the Data Management Plan (DMP).

The DMP will describe the Clinical Data Management System (CDMS) that will be used to collect and validate data. Computerized edit checks and review processes will be performed on an ongoing basis as outlined in the DMP until all data discrepancies are resolved.

After all data discrepancies are resolved, coding is approved, and subject evaluability has been determined, the data will be exported to SAS datasets and will be locked (there will be one lock for Part I and one lock for Part II).

After unblinding (part I only), the locked SAS database will be used to generate subject listings, tabulations and analyses.

The data may be audited by the sponsor and/or CRO Quality Assurance department before or after the first statistical analysis results on the primary criteria.

#### 10.4 QUALITY ASSURANCE / AUDIT / INSPECTION

The clinical trial will be conducted under the sponsorship of GALDERMA R&D in compliance with all appropriate local regulations as well as ICH guidelines and in accordance with the SOPs for clinical trial conduct and monitoring from GALDERMA R&D and/or CRO.

Audits of clinical trial sites may be conducted by GALDERMA R&D /CRO representatives, and inspection may be performed by Regulatory Authority inspectorates or IRBs/ECs before, during, or after the clinical trial.

The investigator will allow and assist the GALDERMA R&D /CRO representatives, IRBs/ECs and any regulatory agency to have direct access to all requested clinical trial-related records.

For the audits performed by, or on behalf of, GALDERMA R&D auditors, audit certificate(s) will be provided by Quality Assurance.

#### 11 ETHICS AND GENERAL CLINICAL TRIAL CONDUCT CONSIDERATIONS

#### 11.1 INSTITUTIONAL REVIEW BOARD (IRB) OR ETHICS COMMITTEE (EC)

This clinical trial protocol will be reviewed and approved by IRBs/ECs prior to clinical trial initiation.

This protocol may be modified at any time for ethical, medical or scientific reasons. Such modifications will be documented by a clinical protocol amendment and, if deemed necessary, an amended protocol will be issued.

Before implementation, the amendment should be submitted and approved by applicable IRBs/ECs and, if required by the Regulatory Authority(ies).

No amendment will be required for modification(s) due to a change in logistical or administrative aspects of the clinical trial (e.g., change in monitors, change of telephone numbers). In such a case, the appropriate institution(s) and/or person(s) will be directly notified of the changes.

#### 11.2 ETHICAL CONDUCT OF THE CLINICAL TRIAL

This clinical trial will be conducted in accordance with the ethical principles originating from the Declaration of HELSINKI declaration (1964) and subsequent amendments, the International Conference on Harmonization (ICH), Good Clinical Practice (GCP) and in compliance with local regulatory requirements.

#### 11.3 SUBJECT INFORMATION SHEET / INFORMED CONSENT

All subjects who participate in this trial will be fully informed about the clinical trial in accordance with the applicable regulations and GCP guidelines and in accordance with local legal requirements.

The Informed Consent Form (including appropriate Assent Form for children (aged 16 to 17) and as applicable, photograph release form or skin replica consent) approved by an IRB/EC, will be fully explained to the subject and parent/guardian if applicable. There will be one ICF for part I (to be signed at the beginning of the trial, before or at the baseline visit) and one ICF for part II (to be signed by the subject at the end of part I, if the subject is considered for part II by the investigator and if s/he is willing to participate to part II).

Prior to any clinical trial procedures, the subject and parent/guardian will sign and date the Informed Consent Form(s) which is written in the local language. A copy of the signed and dated form(s) will

GALDERMA RESEARCH & DEVELOPMENT Protocol N° RD.03.SPR.105061 Page 79 of 99 CONFIDENTIAL

be given to the subject and parent/guardian. The investigator is responsible for maintaining each subject's Informed Consent Form(s) in the investigator's site file (ISF) and providing each subject and parent/guardian with a copy of the consent form.

The Informed Consent Form including photograph release form approved by an IRB/EC will be fully explained to the subject and parent/guardian.

#### 11.4 CONTRACTUAL REQUIREMENTS

A contractual agreement will be signed between the CRO/sponsor and each investigator/institution. This document will contain supplementary information, including financial terms, confidentiality, the clinical trial schedule, third party responsibility, and publication rights.

#### 11.5 DATA COLLECTION AND ARCHIVING

#### 11.5.1 Data Collection

The investigator must maintain required records on all clinical trial subjects.

Data for this clinical trial will be recorded in the subject's source documents, in the product dispensation logs and in the "study companion" tablet allocation log.

All data recorded in the documents described above should be recorded completely, promptly, and legibly using a pen (not a pencil).

Each time a new subject is enrolled, the "study companion" tablet allocation log will be faxed or emailed to Triacys. The real-time data obtained through the "study companion" tablets will be automatically transferred to Triacys servers using specific software elaborated by Triacys. A copy of the videos taken by the subject will be maintained locally by the product dispenser during the trial and eventually destroyed once reconciliation with the central database will have been performed. Special attention will be brought to the videos in order to avoid possible use of those by non-qualified personnel or for reasons other than those related to the trial and indicated in the present protocol.

#### 11.5.2 Source documentation

Investigators must keep accurate separate records (other than the eCRF) of all subjects' visits, and all procedures done, being sure to include all pertinent clinical trial related information from which eCRF data will be recorded.

GALDERMA RESEARCH & DEVELOPMENT Protocol N° RD.03.SPR.105061 Page 80 of 99 CONFIDENTIAL

A statement should be made on subject's medical notes indicating that the **subject has been** enrolled in GALDERMA R&D protocol RD.03.SPR.105061 and has provided dated and signed informed consent and assent if appropriate.

All adverse events with the associated concomitant therapies must be thoroughly documented. Results of any diagnostic tests conducted during the clinical trial will be included in the source documentation.

Telephone conversations with the subjects and/or CRO/GALDERMA R&D concerning the clinical trial may be recorded and kept on file.

Once the images from the "study companion" tablets will have been analyzed by qualified operators from Triacys and the report issued by Triacys finalized, they will be destroyed. In no case, personnel other than the qualified operators will have access to the images. The report will be kept on site in the ISF as transcription of the original source data (the videos).

#### 11.5.3 Archives

All pertinent data, samples, photos, questionnaires, correspondence, original or amended protocol, all reports and all other material relating to the clinical trial will be maintained securely in GALDERMA R&D / Investigator/Institution archives for the legally-required duration of archiving.

If the investigator retires, relocates, or for any other reason withdraws from the responsibility of keeping the clinical trial records, custody must be transferred to a person who will accept the responsibility. The sponsor must be notified in writing of the name and address of the new custodian.

A copy of the trial data obtained via the analysis of the videos taken with the "study companion" tablets (the compliance report) will be maintained for a period of 25 years. By contrast, the images will not be maintained after the analysis is completed and the final compliance report is finalized.

#### 11.6 Insurance

A certificate attesting third party coverage of CRO/GALDERMA R&D will be provided upon request.

#### 13 ATTACHMENTS

#### **13.1 APPENDIX 1**

# SCARS questionnaire (Self-assessment of Clinical Acne-Related Scars)

#### RIGHT-HAND SIDE OF THE FACE

#### Part 1

Please remove all make-up and facial jewellery/piercings, and tie back any loose hair covering your face before answering this questionnaire.

Please begin by answering the questions below. These questions will help you understand the difference between active acne and atrophic acne scars.

a) Active acne includes zits, breakouts, pimples, w	a) Active acne includes zits, breakouts, pimples, whiteheads, and blackheads.				
When looking at the right-hand side of you breakouts , pimples , whiteheads , or blackh	ar face in the mirror right now, do you see zits , eads ?				
Yes / No (please circle one)					
	breakouts, pimples, whiteheads, or blackheads ng a vertical line in the place that best describes				
No active acne	Very severe active acne				
0	10				

The following question asks you about **atrophic acne scars** only. Please do not consider active acne (zits, breakouts, pimples, whiteheads, or blackheads), scabs, or flat red or dark marks.

b) Atrophic acne scars are indents or holes in the skin from previous active acne (not from injury, scratching or picking).				
When looking at the right-hand side of your face in the mirror right no or holes in the skin from previous active acne?	ow, do you see indents			
Yes / No (please circle one) If you answered "No" for this question, please go to page 4 to answe hand side of your face.	r questions for the left-			
If yes, please rate the severity of the indents or holes on the right-ha putting a vertical line in the place that best describes your scars.	nd side of your face by			
No indents Very severe or holes indents or holes				
0	10			

#### Part 2

The following questions ask you about **atrophic acne scars only**. Remember, atrophic acne scars are **indents or holes** in the skin from previous active acne. Please **do not** consider active acne (zits, breakouts, pimples, whiteheads, or blackheads), scabs, or flat red or dark marks.

Please read each question, then look in the mirror and think about the indents or holes on the **right-hand side of your face**, and then answer the question. Please mark an "X" in the box  $(\boxtimes)$  that best describes how the indents or holes on your face look **RIGHT NOW**.

There are no right or wrong answers to these questions. If you want to change your answer, please cross out your original answer and mark an "X" in the correct box.

Please choose only one response.

1. When looking at the right-hand side of your face in the mirror right now, how much of your face looks covered by indents or holes?

Almost none	A little	Some	A lot	Almost all
of the right-hand				
side of face				

